The women with PCOS will be stratified according to whether they are insulin resistant or non insulin resistant based upon the results of their glucose tolerance test. Both groups will be randomized to receive the drug flutamide 125 mg/day or placebo. Subjects will take the drug/placebo every day for 6 - 28 day cycles and will continue to take the drug/placebo until all post treatment assessments are completed. Subjects will be asked to collect and store a urine sample once a week during the 6 - 28 day cycles. Subjects will also be asked to complete diaries. Once a month while they are taking the flutamide/placebo, they will return to the clinic and bring their urine samples. At that time they will undergo a physical exam, toxicity assessment, and blood draw. Quality of Life surveys will be performed at baseline, midpoint, and end of study for PCOS participants. Non-PCOS participants will complete Quality of Life surveys at baseline only.

After the 6 - 28 day cycles are completed the PCOS participants will continue to take study drug/placebo until they have completed end of treatment evaluations which include physical exam, additional blood tests, removal of abdominal fat, trasvaginal ovarian ultrasound, MRI, DXA scan, frequently-sampled intravenous glucose tolerance test (FSIGT), and follicle stimulating hormone stimulation test.

Per amendment #11 submitted 11-25-13, subjects who previously underwent an OGTT will be asked to undergo an FSIGT. Women enrolled on the PCOS arm may choose to decline the FSIGT and will undergo an OGTT post treatment.

Per Amendment #24 submitted 6/10/15, we requested permission to add a Family History Questionnaire to this study. Subjects who have been enrolled in the past as well as future participants will be asked to complete the questionnaire. Active study participants will be asked to complete the questionnaire at their next regularly scheduled study visit. Those who have completed all of their study visits will be contacted by phone or email to ask if they will complete the questionnaire. If they agree, it will be sent to the participant by US mail with a stamped return envelope or the questionnaire will be completed over the phone. New study participants will be asked to complete the questionnaire at their eligibility visit. If any participant(s) decline, their participation in Revised 3-7-18 UCLA IRB #12-001780 Page 3 of 27

this study will not be affected nor will their future healthcare at UCLA.

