BACKGROUND AND SIGNIFICANCE

Polycystic ovary syndrome (PCOS): PCOS, a common endocrinopathy affecting 6–10% of women, manifests by hyperandrogenism, ovulatory dysfunction and polycystic ovaries (PCO) in its complete phenotype. Abdominal adiposity occurs frequently in PCOS women vs. controls, including some, but not all, nonobese individuals. Consequently, the estimated prevalence of MBS in PCOS is 33-47%, about 2-3 times higher than that of age-matched controls.

Interplay between adipose function and androgen excess: In PCOS, intrinsic defects combine with endocrine factors to impair insulin sensitivity and induce adipocyte insulin resistance (IR). Conversely, physiological androgen administration to women induces IR. In PCOS women, therefore, androgen excess could decrease numbers of SC abdominal adipocytes and reduce capacity of this adipose to safely store fat. Thus, if energy intake exceeds this capacity, SC abdominal adipocytes would likely overfill with lipid to promote ectopic lipid deposition. We hypothesize that PCOS-related hyperandrogenism decreases adipogenic differentiation and increases adipocyte lipid content in a constrained SC abdominal adipose, inducing lipotoxicity, IR and ovulatory dysfunction.

Therefore, reducing PCOS-related androgen excess could improve SC abdominal adipogenic function and ovarian folliculogenesis, reducing use of ovulation-inducing agents in PCOS women wishing to conceive, and risks of multiple pregnancy.

Effect of flutamide on PCOS: Administration of flutamide, a nonsteroidal anti-androgen, to PCOS women lowers circulating androgen and triglycerides levels. Flutamide also restores ovulation in some, but not all, PCOS women. We will systematically compare SC abdominal adipogenesis, circulating adipogenic markers and SC abdominal as well as visceral (omental plus mesenteric) adipose content of lean PCOS women randomized to 6-month low-dose flutamide vs. placebo to determine how differences in key variables affect ovarian function and morphology, as well as in vivo E2 responsiveness to FSH.

We also are able to quantify SC abdominal and visceral adipose content by magnetic resonance imaging (MRI), as performed by [name]. Finally low-dose flutamide vs, placebo administration to lean PCOS women will discover novel molecular and biochemical markers that predict efficacy of androgen blockade in restoring adipogenic and ovarian function.

AIMS AND OBJECTIVES

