iii). Body fat distribution: Total body DXA will measure abdominal fat (i.e., the area between the dome of the diaphragm [cephalad limit] and the top of the greater trochanter [caudal limit]). Total body DEXA images also will determine % body fat; fatfree body mass; total body, abdominal, and leg fat; and abdomen/leg fat mass ratio. The leg region is that area below the top of the greater trochanter. Multiple axial abdominal and pelvic MRI slices from the diaphragm to the pelvis will assess cross-sectional areas of SC abdominal and visceral fat.

iv). Ovarian testing:

a). Ovarian morphology: TVUS using a 4- to 8-mHz vaginal probe will be performed in the follicular phase in controls and during amenorrhea in PCOS women. Summed ovarian volume will be calculated. Antral follicle number, defined as the total follicle number (2-9 mm in diameter) of both ovaries, will be determined by 1 investigator ([name]). Polycystic ovaries will be defined by 12 or more follicles in each ovary measuring 2-9 mm in diameter, and/or increased ovarian volume (> 10 ml), with one such ovary sufficient to define PCO.

b). E2 response to recombinant human (rh)FSH. Blood samples will be drawn through an indwelling iv catheter at -90, -60, -30 minutes and time 0 as well as 0.5, 1, 1.5, 2, 3, 4, 6, 8, 10, 12, 16, 20, and 24 h after 150 U rhFSH injection (112). The E2 response to rhFSH will be assessed before and after adjusting for numbers of TVUS-detected ovarian antral follicles.

Aim 2. Examine effect of flutamide in lean PCOS women on SC abdominal adipogenesis, visceral adipose content and ovarian folliculogenesis.

Per amendment #29, we are requesting permission to change the randomization strategy since all PCOS subjects enrolled thus far have been non-insulin resistant

Revised 3-7-18 UCLA IRB #12-001780 Page 7 of 27

based upon the results of the Frequently Sampled Intravenous Glucose Tolerance Test. Therefore, the need to stratify the PCOS subjects into two groups (i.e. insulin resistant versus non-insulin resistant) is unnecessary. All PCOS subjects recruited will now be randomized to study drug versus placebo based upon non-insulin resistant status. Of note, the control subjects are not randomized since they do not receive study drug or placebo.

Adipogenic studies: All adipogenic studies performed at study initiation will be repeated at the end of the 6 - 28 day cycles of flutamide vs. placebo intervention in PCOS women.

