We will use one-way factorial analysis of variance (ANOVA) methods to compare continuous outcomes including hormone levels; adipocyte size, lipid content and glycerol release; numbers of ASCs and preadipocytes; mRNA levels. If data are not normally distributed on any scale, we will carry out nonparametric ANOVA.

Our previous comparison of cFOS gene expression in PCOS women vs. controls showed an increase in Δ Ct (6.0 ± 1.4). Based on this, we hypothesize that the mean difference between controls and IR PCOS is 1.7 SD units. Assuming this, a sample size of 8/group (IR vs. non-IR PCOS) provides over 80% power using the usual two-sided p < 0.05.

We also will compare all outcomes before vs. after 6 months of placebo or flutamide treatment controlling for IR status, using either the parametric paired t test or non-parametric Wilcoxon signed rank test. Insulin action and sensitivity will be assessed by calculating a Matsuda Index from blood glucose and insulin levels during the oral glucose tolerance test. Ovarian estradiol sensitivity to FSH will be calculated from the 24-hr area-under-the-curve (AUC) serum estradiol response to FSH infusion.

Based on our in vitro data, we observed a mean 0.17 log scale change in Δ Ct PPAR γ (SD=0.26 log units) after treatment with T + Flutamide vs. T alone. A sample size of 14 (7 non-IR, 7 IR) provides more than 80% power for the IR adjusted mean change.

REFERENCES

3. 2004. Revised 2003 consensus on diagnostic criteria and long-term health risks related to polycystic ovary syndrome. Fertil Steril 81(1):19-25.

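### The power statements still assume insulin-resistant PCOS women, although amendment #29 reports none enrolled and drops the split; Aim 1's own contrast, PCOS vs. controls, has no stated power

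*Combined protocol and SAP*

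**What the plan says.** Aim 1 (Aims and Objectives) compares lean PCOS women with age- and BMI-matched controls. Its hypothesis is that subcutaneous abdominal fat storage is constrained in lean PCOS. Planned completers are 36 PCOS women and 12 controls (Research Design and Methods; Inclusion Criteria).

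Statistical Considerations starts from earlier cFOS expression data in PCOS women vs. controls (ΔCt 6.0 ± 1.4), with no mention of a split by insulin resistance. It then says "we hypothesize that the mean difference between controls and IR PCOS is 1.7 SD units", and in the next sentence that "a sample size of 8/group (IR vs. non-IR PCOS) provides over 80% power using the usual two-sided p < 0.05". For Aim 2, it plans before/after comparisons adjusted for IR status and gives a sample size of 14, made up of 7 non-IR and 7 IR women.

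The amendment #29 paragraph under Aim 2 changes the randomization "since all PCOS subjects enrolled thus far have been non-insulin resistant". It calls stratification by IR unnecessary and randomizes all PCOS recruits on non-IR status. The Lay Summary still reads "The women with PCOS will be stratified according to whether they are insulin resistant or non insulin resistant", with both strata randomized.

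**The concern.** This is a conflict within the current text. The document is dated March 2018 and already carries amendment #42, yet Statistical Considerations was not brought into line with amendment #29.

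Three things follow:

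- The one power statement built on PCOS-vs-control data is for a comparison with one group empty at amendment #29.
- Its effect size belongs to a different pair of groups from those it is applied to, and neither pair is the Aim 1 contrast.
- The Aim 2 analysis adjusts for a factor that did not vary among the women enrolled up to that amendment, and its sample size assumes women who had not been found.

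As written, a reader cannot tell what difference the Aim 1 comparison can detect, which population the conclusions cover, or, from the Lay Summary, which randomization scheme is in force.

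**Working it through.** **Inputs from the documents.** Difference 1.7 SD, 8 per group, two-sided 0.05, power stated as over 80% (Statistical Considerations). No IR women among PCOS enrollees as of amendment #29 (Aim 2). Completers: 36 PCOS and 12 controls.

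**Method.** Two-sample t test with noncentrality δ = d / √(1/n₁ + 1/n₂) and df = n₁ + n₂ − 2. Power is the probability that a noncentral t exceeds the two-sided 5% critical value.

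**Step 1: the plan's own figure.** With 8 vs. 8 and d = 1.7: δ = 1.7 / √(1/8 + 1/8) = 3.40, df = 14, critical value 2.145, power 88.5%. The normal approximation gives 92.5%. Both exceed 80%, so the stated figure reproduces. The fault lies in the groups.

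**Step 2: which groups does it describe?**

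| Element | Contrast named | Needs IR women? |
|---|---|---|
| Source data (cFOS) | PCOS vs. controls | not split by IR |
| Hypothesised 1.7 SD | controls vs. IR PCOS | yes |
| 8 per group | IR vs. non-IR PCOS | yes |
| Aim 1 | lean PCOS vs. controls | no |

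With 0 women in the IR group, 1/n₁ is undefined and the test cannot be run. The mismatch would matter even with IR women present. If the IR vs. non-IR difference were half of 1.7 SD (0.85, an assumption), 8 per group would have 35% power.

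**Step 3: the Aim 1 contrast.** With 36 vs. 12: √(1/36 + 1/12) = 0.333, so δ = 3d, with df = 46 and critical value 2.013.

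| Difference (SD) | δ | Power |
|---|---|---|
| 1.7 | 5.10 | 99.9% |
| 1.0 | 3.00 | 83.6% |
| 0.954 | 2.86 | 80.0% |
| 0.85 | 2.55 | 70.4% |
| 0.7 | 2.10 | 53.8% |

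Only 1.7 comes from the plan, and there it is for controls vs. IR PCOS. The row at 0.954 is solved from the sample size; the others are assumed effects. The plan gives no expected difference for non-IR PCOS vs. controls.

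**Step 4: Aim 2.** If every woman is non-IR, an IR covariate is a constant and its coefficient cannot be estimated, so the adjustment does nothing. The 7 + 7 split describes a sample that amendment #29 no longer plans for.

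**The case against.** The best reply is that this is stale text with limited consequences. Aim 1's hypothesis contains no IR class. Insulin is examined by correlating key factors with insulin action in vivo, and Statistical Considerations uses a continuous index. The amendment #29 paragraph gives the operative randomization. All of this stands: only the IR vs. non-IR contrast and the power statement attached to it are lost.

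The amendment's wording is also dated. It speaks of women enrolled thus far and gives no count, so later IR women are not ruled out. A few could go some way: among 36 PCOS completers, an assumed 3 IR women would give 78% power against the other 33 at 1.7 SD, and 4 would give 88%. But the plan now makes no provision for them, and its own sentence asks for 8.

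Three stronger readings are tempting and are not supported:

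- **That the insulin part of the hypothesis is now untestable.** Background and Significance does propose that androgen excess "increases adipocyte lipid content in a constrained SC abdominal adipose, inducing lipotoxicity, IR and ovulatory dysfunction", but variation in insulin sensitivity can still be studied in non-IR women through the planned correlations.
- **That 1.7 SD is too large for non-IR women.** No figure in the documents shows a smaller effect in them, and the source data were PCOS vs. controls overall. The effect in non-IR women is unstated, which is a different criticism.
- **That the trial has no IR women at all.** The documents support this only as of amendment #29.

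**Conclusion.** The point holds as a failure to update the statistical section, and it should be corrected. The 88.5% power behind the plan's claim belongs to a comparison that could not be made with the women enrolled at amendment #29. The Aim 2 adjustment and its 7 + 7 sample size fail for the same reason. Aim 1's contrast has no stated power. With 36 and 12 completers it reaches 80% only for differences of about 0.95 SD or more.

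This rests on the planned completer numbers being met, a t test on roughly normal outcomes with equal variances, and no allowance for multiple outcomes. Whether 0.95 SD is a plausible difference cannot be judged from the documents, so the calculation does not show that Aim 1 is adequately powered.

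**What to change.** 1. Replace the 8-per-group sentence with the Aim 1 contrast: 12 controls vs. 36 PCOS completers, two-sided 0.05, 80% power for a difference of about 0.95 SD. Label this as the detectable difference, and show about 70% at 0.85 SD and 54% at 0.7 SD as assumed effects. If the sponsor has a rationale for an expected effect in non-IR women, state it.
2. Delete the adjustment for IR status from the before/after analysis. Restate the 14-woman sentence for a non-IR sample, recomputing its power rather than only relabelling the groups. On one simple reading (paired t test, with 0.26 the SD of the change), 0.17/0.26 = 0.654 and n = 14 give δ = 0.654 × √14 = 2.45 and power of about 62%, so the over-80% figure should not be carried over unchecked.
3. State that insulin sensitivity is analysed as a continuous variable, as Aim 1's correlations already imply.
4. State that conclusions apply to lean, non-insulin-resistant PCOS if no IR women are enrolled.
5. Reconcile the IR-stratified randomization in the Lay Summary with the amendment #29 paragraph.

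No new participants or procedures are needed for these edits. The cost is a narrower claim, a less favourable stated detectable effect, and some work if an expected effect is to be justified.

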Per amendment #42, epigenetic studies (RNA sequencing, DNA Methylation, and Assay for Transposase Accessible Chromatin Sequencing) on existing fat cell samples will be conducted at UCLA.

INCLUSION CRITERIA

Caucasian and Non-Hispanic women between the ages of 18 to 35 years.

Groups will be: 12 lean controls (Aim 1); 36 age- and BMI-matched PCOS women randomized to flutamide vs. placebo for 6 months (Aims 1 and 2).

i) Lean patients with PCOS: 36 subjects with PCOS (defined by 1990 NIH criteria [all Aims]), BMI 18.5-25 kg/m2. This BMI range is defined as normal and has been chosen to examine underlying mechanisms of PCOS-related androgen excess in the genesis of adipogenic and ovarian dysfunction, independent of obesity. Excessive course hair on upper lip, chin, chest, upper back, lower back, upper abdomen, lower abdomen, arm and/or thigh.

ii) Lean control women: 12 healthy subjects, BMI 18.5-25 kg/m2. Controls will have regular menstrual cycles, and no evidence of hirsutism, acne, alopecia, polycystic ovaries, and/or endocrine dysfunction. This BMI range has been chosen to match that of the PCOS group.

Up to 70 lean PCOS patients and 20 lean controls will be recruited, for a total of 90 study participants over a 5-year interval, accounting for a 20% rate of patient drop-out or insufficient adipose procurement. Participants must be fluent in English.

EXCLUSION CRITERIA

Exclusion criteria for study participation are: present or past history of smoking within past 1 year, cancer, alcohol abuse within past 5 years, drug addiction within past 5 years, severe depression within past 5 years, or post traumatic stress disorder within

Revised 3-7-18 UCLA IRB #12-001780 Page 10 of 27

past 5 years; diabetes; uncontrolled hypertension (≥ 165/100); clinically significant hepatic or renal disease, or other major medical illness; recent (within 3 months) use of androgens, anabolic steroids or hormonal agents (including birth control pills or insulin sensitizers), Mirena IUD, or Plan B contraception. These exclusion criteria are chosen to avoid effects from medical conditions, environmental factors or exogenous agents. Women taking the drug warfarin, beta blockers, CYP active medications, or herbs will be excluded.

Since this study involves MRI testing, women with pacemakers, metal implants, or claustrophobia will be excluded.

The screener will assess the participants response to establish if depression or drug use exclude participation in this study.

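### The statistical section states no flutamide-versus-placebo test; its only treatment-period analysis is before versus after, which cannot isolate the drug effect or be applied to ovulatory frequency

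*Combined protocol and SAP*

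**What the plan says.** The design is a randomized comparison. Background and Significance describes comparing adipogenesis, circulating markers and "adipose content of lean PCOS women randomized to 6-month low-dose flutamide vs. placebo". Under Aim 2, amendment #29 keeps the randomization but drops stratification by insulin resistance (IR), because every PCOS woman enrolled so far was non-resistant: "All PCOS subjects recruited will now be randomized to study drug versus placebo based upon non-insulin resistant status".

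Statistical Considerations contains two analyses and two sample-size statements:

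- **ANOVA.** "We will use one-way factorial analysis of variance (ANOVA) methods to compare continuous outcomes including hormone levels". No grouping factor or time point is given. The sizing that follows concerns controls, IR PCOS and non-IR PCOS.
- **Before-after test.** "We also will compare all outcomes before vs. after 6 months of placebo or flutamide treatment controlling for IR status". It is not said whether this is run in each arm or on both arms together. One of two methods is to be applied, the choice being worded as "using either the parametric paired t test or non-parametric Wilcoxon signed rank test".
- **Aim 2 sizing.** From an in vitro change of 0.17 log units (SD 0.26), 14 women (7 non-IR, 7 IR) are said to be enough: this "provides more than 80% power for the IR adjusted mean change".

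Aims and Objectives makes ovulatory frequency, measured by weekly urinary pregnanediol glucuronide (UPDG), an Aim 2 outcome. The Lay Summary and Procedures place the weekly urine collection in the six treatment cycles. The start-of-study procedures listed under Aim 1 include no urine series.

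**The concern.** A paired test asks whether women changed. It does not ask whether women on flutamide changed more than women on placebo, which is the Aim 2 question. Shared change is plausible here: women are enrolled because of abnormal hormone and menstrual findings that may regress, they keep daily diet and exercise diaries, and the second biopsy is taken from the opposite side. Followed literally, the plan could report a flutamide effect that placebo also shows, and it gives no estimate of the difference.

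For ovulatory frequency the stated test cannot be run, because there is no pre-treatment UPDG series. Baseline information on ovulation consists of menstrual history and single progesterone checks at test visits, which are a different measurement.

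**Working it through.** **1. What each stated analysis estimates.** Let τ be the drug effect and δ the change common to both arms.

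- Paired test in the flutamide arm: tests τ + δ = 0.
- Paired test in the placebo arm: tests δ = 0.
- Paired test on both arms pooled (1:1): tests τ/2 + δ = 0.
- Difference between arms in change: (τ + δ) − δ = τ.

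Only the last isolates τ, and it is not among the stated analyses. Nor does either named paired test take a covariate, so IR status could not be controlled for in it even if it still varied.

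**2. The plan's own Aim 2 figure.** d = 0.17/0.26 = 0.654. For a paired t test with n = 14 and two-sided 0.05 (the level stated for the cFOS sizing, assumed here), the noncentrality is 0.654 × √14 = 2.446 on 13 df, giving 61.9% power; with one df spent on IR, 61.3%. More than 80% is not reproduced; a paired test needs n = 21 (81.3%). This is a separate problem, but it confirms that the sizing concerns a single-sample change.

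**3. Power of the missing contrast.** Assumptions: 0.17 is the arm difference, allocation is 1:1 (the ratio is not stated), and baseline and final variances are equal with correlation r. Completers: 36 (Subjects and clinical assessment; Inclusion Criteria), i.e. 18 per arm. Alternatively, up to 70 recruits "accounting for a 20% rate of patient drop-out or insufficient adipose procurement" gives 70 × 0.80 = 56, i.e. 28 per arm.

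Two-sample test of change, with 0.26 as the SD of change: noncentrality 0.654 × √(n/2).

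- 18 per arm: 0.654 × 3 = 1.962, 34 df, power **47.9%**.
- 28 per arm: 0.654 × √14 = 2.446, 54 df, power **67.1%**.
- 80% needs 38 per arm.

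ANCOVA on baseline has 2n − 3 df. The residual SD is (a) 0.26 × √((1 + r)/2) if 0.26 is the SD of change, or (b) 0.26 × √(1 − r²) if it is the SD of the outcome. For example, in (a) at r = 0.5 the residual SD is 0.26 × √0.75 = 0.225 and the noncentrality at 18 per arm is (0.17/0.225) × 3 ≈ 2.265, giving 59%.

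| r | (a) 18/arm | (a) 28/arm | (b) 18/arm | (b) 28/arm |
|---|---|---|---|---|
| 0 | 77% | 92% | 48% | 67% |
| 0.3 | 66% | 85% | 51% | 71% |
| 0.5 | 59% | 79% | 59% | 79% |
| 0.7 | 54% | 74% | 76% | 92% |
| 0.9 | 50% | 69% | 99% | >99% |

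Under (a), ANCOVA reaches 80% with 20, 25, 29, 33 and 36 per arm for these r.

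**4. Illustration of the error.** The documents give no drift size, so these values are assumptions. Set τ = 0 and let both arms drift by the same number of SDs of change.

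| Shared drift | Flutamide paired test significant, 18/arm | 28/arm | Flutamide significant and placebo not, 18/arm | 28/arm |
|---|---|---|---|---|
| 0 | 5% | 5% | 5% | 5% |
| 0.2 SD | 13% | 18% | 11% | 14% |
| 0.5 SD | 52% | 72% | 25% | 20% |

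The right-hand pair is p(1 − p), where p is the matching paired-test probability and the arms are independent. A direct between-arm test stays at 5% in every row.

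**The case against.** The strongest reply is that this is under-specification. The background clearly intends an arm comparison, and an ANOVA without a named factor could be used for one. That reading is possible. But the ANOVA is not tied to arms, to change or to the end of treatment, and it covers continuous outcomes only. The treatment paragraph is introduced as an additional analysis with its own tests, and the Aim 2 sizing follows it.

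A second reply is that the 52% and 72% overstate the risk, since a paired test in the placebo arm would also reveal the drift. That is fair if the test is run per arm and the two results are read together. The error is then 25% and 20% at 0.5 SD, still well above 5%. Some of the suggested sources of drift are also conjectural: the diaries are not an intervention, screening does not select on adipose gene expression, and nothing says the two sides of the abdomen differ.

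Third, the power table is wide and rests on an in vitro effect. The protocol's firmer expectation is 36 completers, and the wording favours reading 0.26 as the SD of change. The Lay Summary's 50 PCOS women, less 20%, would give 20 per arm and 52% on change scores. All of this stands, but the omission does not depend on the power figures.

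Fourth, early and late treatment cycles could be paired for UPDG. They could, but that is not a comparison with the period before treatment. One stretch of the methods text was not available to check for a baseline urine collection; the statistical section was.

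**Conclusion.** The concern holds and needs correcting. The central comparison of a randomized, placebo-controlled aim has no stated test; the before-after test offered for the treatment period does not estimate the drug effect and cannot be applied to UPDG-based ovulatory frequency. This conclusion rests on the text alone.

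The size of the power shortfall is conditional. With 36 completers split equally and 0.26 as the SD of change, the arm contrast is below 80% at every correlation from 0 to 0.9. With 56 completers, or with 0.26 as the outcome SD, it may or may not reach 80%. The plan settles neither the number of completers, nor the allocation ratio, nor the meaning of the SD, nor the correlation.

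**What to change.** In Statistical Considerations, ideally before unblinding:

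- Make the Aim 2 inference the flutamide-minus-placebo difference with a 95% CI, from ANCOVA of the end-of-treatment value on arm and baseline. A two-sample test of change would also cure the defect. Name a rank-based version for non-normal outcomes, and keep the paired tests as descriptive.
- Compare on-treatment UPDG-confirmed ovulation between arms by an exact or rank test, or by a count model with an offset for cycles observed.
- State the ANOVA's grouping factor and time point.
- Remove the IR adjustment and the 7 + 7 split.
- For insulin action, say how women with OGTT pairs and women with FSIGT pairs are combined, since their baselines are on different scales.
- Restate the Aim 2 power for the arm contrast, giving the allocation ratio, the expected completers and which SD 0.26 is.

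The cost is wording. Baselines are already scheduled for the continuous outcomes, and urine is collected in both arms. The drawback is a stated power that is probably less favourable than the present claim.
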